5.2 INCLUSION CRITERIA

- 1) Male subjects aged between 18 and 40 years.
- 2) Body mass index (BMI) between 19 and 25 kg/m²
- 3) Volunteers whose investigations (ECG, chest X-ray, blood and urine, PCR for COVID-19), performed prior to their inclusion and are within normal limits and/or without clinical significance at the investigator's discretion.
- 4) Subjects with systolic blood pressure higher than 110 mm Hg and lower than 139 mm Hg, a diastolic pressure higher than 70 mm Hg and lower than 89 mm Hg with a heart rate higher than 50 and lower than 90 beats per minute after being 5 minutes in a sitting position and then in a standing position (outliers included).
- 5) Volunteer being willing to participate in the study and who has signed the informed consent approved before the study initiation.

5.3 EXCLUSION CRITERIA

- 1) History of clinically significant allergies (except asymptomatic untreated seasonal allergies),
- 2) ≥ 20 mm Hg drop in systolic pressure or ≥ 10 mm Hg in diastolic pressure in the first 3 minutes of postural change.
- 3) Volunteers who are or have been taking other drugs (prescription or over-the-counter) within two weeks prior to the study.
- 4) Volunteers with a history of autoimmune diseases.
- 5) Organic CNS mental and/or psychiatric conditions: bipolar disorder, severe depression, insomnia, changes in personality.
- 6) Active or chronic infections
- 7) Reception of live or dead virus, bacteria vaccines within fifteen days prior to visit 1 or 2.
- 8) In the case of COVID vaccines, a window period longer than 15 days must be observed before visits 1 or 2. This period is contemplated based on the recommendations by the National Ministry of Health published on 5-29-2021. The volunteer may receive the vaccine 35 days after receiving the investigational product.
- 9) Known allergy to any of the components of the formulations.
- 10) Active smoker of more than 10 cigarettes/day.
- 11) Current clinical evidence of severe digestive disorders, digestive tract surgeries (except appendectomy)
- 12) Current clinical evidence of kidney disease.
- 13) Current evidence of liver disorders
- 14) Current clinical evidence of respiratory and cardiac diseases.
- 15) Presence of diabetes mellitus, thyroid dysfunction or other endocrine disorder.
- 16) Evidence of active gastroduodenal disease.
- 17) History of peripheral thrombotic phenomena
- 18) Underlying neurological disease
- 19) Current presence of any progressive chronic disease
- 20) History of drug or alcohol abuse or addiction during the last three years.
- 21) Participation in a clinical study within the last three months.
- 22) Use of any drug within fourteen days prior to the study initiation that, at the principal investigator's discretion, may interfere with the drug biodistribution.

- 23) Subject who donated or experienced blood loss within the last twelve weeks prior to the study initiation, or willing to donate blood within three months after the end of the study.
- 24) Excessive drinker of tea, cocoa, mate, coffee and/or beverages containing caffeine (>5 cups/day) or wine (>0.5 L/day) or alcoholic drinks (>50 ml/day).
- 25) Significant abnormalities in the electrocardiogram
- 26) PCR positive for COVID-19
- 27) Serology positive for HIV, hepatitis B or hepatitis C.
- 28) Abnormal clinical laboratory results (which, at the principal investigator's discretion, are considered clinically significant)
- 29) Non-cooperative volunteer

5.4 STUDY WITHDRAWAL CRITERIA

Subjects may freely withdraw from the study at any time, and without giving reasons. For safety, behavior or administrative reasons, they may also be withdrawn from the study, at the Principal Investigator's discretion. If a subject does not come for the next scheduled visit, every effort should be made to contact the subject, document the reasons for his withdrawal, and ask for any adverse events.

If the subject decides to withdraw during the study, the safety telephone follow-up will be made on days 3, 7, 14 and 21. The investigator may retain and continue using any data collected prior to the withdrawal of consent.

A patient will be withdrawn from the study due to any of the following causes:

1. If you have study drug related- adverse events considered unacceptable.
2. Free decision by the volunteer who no longer wishes to participate in the study without any type of reason
3. Serious adverse event
4. Decision by ANMAT
5. Decision by the Sponsor, or Ethics Committee at DIM CLINICA PRIVADA Site.
6. Risk to the volunteer
7. Decision by the principal investigator, who considers the volunteer is at undue risk
8. Participant who has the possibility of receiving the first or second dose of the COVID vaccine during the study.
9. If the study doctor thinks that continuing in the study may not be at patient's health best interest.
10. If the Sponsor, the Argentine Public Health authority (A.N.M.A.T.) or other applicable regulatory authorities decide to discontinue the study.

11. Non-compliance by the volunteer
12. Not meeting the inclusion criteria or meeting some exclusion or withdrawal criteria at the time of hospitalization.

6 STUDY DRUG

6.1 DRUG NAME, FORMULATION AND STORAGE

6.1.1 Study Formulations

Test Formulation (T)

Biosidus beta agalsidase. Powder for concentrate for solution for infusion. It is supplied as both 35 mg and 5 mg per vial to adjust for the indicated dose

The following data will be specified on the labels of the infusion vials: Lot, Study and expiration date.

Qualitative-quantitative formula:

Biosidus beta agalsidase 35 mg: Each vial contains lyophilized powder to reconstitute:

Drug Substance	Agalsidase beta	35 mg
Inactive ingredients	Sodium phosphate monobasic anhydrous	42 mg
	Sodium Hydroxide	q.s. pH 6.8
	Mannitol	210 mg

Once reconstituted with 7.2 mL WFI, each vial contains 5 mg/mL (35 mg/7 mL) agalsidase beta. Reconstituted solution must then be diluted.

Biousidus agalsidase beta 5 mg: each vial contains lyophilized powder to reconstitute:

Drug Substance	Agalsidase beta	5.5 mg
Inactive ingredients	Sodium phosphate monobasic anhydrous	6 mg
	Sodium Hydroxide	q.s. pH 6.8

	Mannitol	30 mg
--	----------	-------

Once reconstituted with 1.1 mL WFI, each vial contains 5 mg/mL agalsidase beta. Reconstituted solution must then be diluted.

Reference Formulation (R)

Sanofi-Genzyme Fabrazyme®. Powder for concentrate for solution for infusion. It is supplied as both 35 mg and 5 mg per vial to adjust for the indicated dose.

The following information shall be specified on the labels of infusion bottles: Lot, Study and expiration date.

Qualitative-Quantitative Formula:

Fabrazyme® 35 mg: each vial contains lyophilized powder to reconstitute:

Drug Substance	Agalsidase beta	37 mg
Inactive ingredients	Sodium phosphate monobasic monohydrate	20.4 mg
	sodium phosphate dibasic heptahydrate	59.2 mg
	Mannitol	222 mg

Once reconstituted with 7.2 mL WFI, each vial contains 5 mg/mL (35 mg/7 mL) Fabrazyme® agalsidase beta. Reconstituted solution must then be diluted.

Fabrazyme® 5 mg: each vial contains lyophilized powder to reconstitute:

Drug Substance	Agalsidase beta	5.5 mg
Inactive ingredients	sodium phosphate monobasic monohydrate	3 mg
	sodium phosphate dibasic heptahydrate	8.8 mg
	Mannitol	30 mg

Once reconstituted with 1.1 ml WFI, each vial contains 5 mg/mL Fabrazyme agalsidase beta. Reconstituted solution must then be diluted.

Justification for the difference in drug substance Agalsidase Biosidus and Frabrazyme® strengths is found in Annex 7.

6.1.2 Content and Potency Uniformity

Prior to the clinical phase of this study, the Biosidus Development Department will evaluate the comparative enzyme activity of all batches of the Test and Reference products to be used in the clinical study. Content uniformity of the formulations will also be determined by reverse phase HPLC.

Justification for the difference in drug substance Agalsidase Biosidus and Frabrazyme® strengths is found in Annex 7.

6.1.3 Storage

All the medication for this study will be stored in the refrigerator at 2 °C – 8 °C, not in the freezer, under adequate conditions, indicated by the sponsor in writing, with restricted access to the staff in charge.

6.2 MATERIAL PREPARATION AND LABELING

Medication used in the study will be provided by Biosidus S.A., in accordance with current regulations. Preparation for the medication used for each volunteer will be made by the principal investigator, or his designee, as follows.

Each volunteer will receive one (1) intravenous infusion in the arm. Vials will be labeled with a self-adhesive label where the study code and other information necessary for the label of the investigational product will be mentioned, in accordance with ANMAT Provision 6677/2010, as indicated in Annex 3. Reconstitution and dilution for each volunteer will be made based on his body weight.

6.3 DOSE AND ROUTE OF ADMINISTRATION

Each volunteer will receive a single 1 mg/kg agalsidase beta dose.

To adjust the required dose based on the volunteer's weight on the hospitalization day, the following formulations will be available:

1. Fabrazyme® 35 mg lyophilized powder to be reconstituted for infusion
2. Fabrazyme® 5 mg lyophilized powder to be reconstituted for infusion
3. Biosidus Agalsidase 35 mg lyophilized powder to be reconstituted for infusion
4. Biosidus Agalsidase 5 mg lyophilized powder to be reconstituted for infusion

6.4 TREATMENT DURATION

Study duration will be approximately 56 days for each volunteer, assuming: 21 days for the screening period (Visit 1), 1 day for hospitalization and treatment (Visit 2), 4 telephone contacts (days 3, 7, 14 and 21 - Visit 3, 4, 5 and 6) and 1 day for the Final Visit (day 35 – End of study).

Each volunteer will receive only one study formulation (T or R) at visit II (Hospitalization).

7 ENZYME ACTIVITY ANALYSIS

For measurement of the biological enzyme activity in plasma samples, the fluorimetric method of hydrolysis of the synthetic substrate 4MU-Gal will be used.

7.1 PHARMACOKINETIC ANALYSIS OF RESULTS

From the results of plasma concentration of agalsidase beta at the different sampling times, the following variables will be calculated:

ABC_{0-t} : Area under the plasma concentration curve between time 0 and time t (in this case 12 hours).

$ABC_{0-\infty}$: Area under the plasma concentration curve, result of extrapolation between time 0 and time ∞ .

C_{max} : Peak plasma concentration of agalsidase beta.

T_{max} : Time to reach the peak plasma concentration of agalsidase beta.

$C_{max} / ABC_{0-\infty}$: ratio between the peak plasma concentration and the area under the plasma concentration curve between time 0 to ∞ , as an absorption rate index of less variability than the T_{max} .

The drug elimination constant and elimination half-life in the body will be calculated. The summary measures (arithmetic and geometric means, standard deviation, CV% and range) for each infusion will be presented, as well as the individual results of each volunteer.

7.1.1 Comparative pharmacokinetic analysis between formulations

ABC_T/ABC_R : Ratio between the area under the curve of each test formulation and the area under the curve of the reference formulation.

For logarithmic transformation, the 90% confidence interval of the AUC ratio (for $ABC_{0-120\text{ h}}$ and $ABC_{0-\infty}$) should be within the range of 0.80-1.25.

$C_{max\ T}/C_{max\ R}$: Ratio between the C_{max} of each Test formulation and C_{max} of the Reference formulation. For logarithmic transformation, the 90% confidence interval of the C_{max} ratio should be first within the range 0.80-1.25 (80% to 125%). Considering the high intra-individual variability of this pharmacokinetic parameter, if a variability > 30% is confirmed, this interval for the C_{max} may be extended to 0.75-1.33 (75-133%).

The FDA assumes that the test product is considered bioequivalent to the reference product if the 90% confidence interval (CI) of the geometric mean ratio of AUC and C_{max} between the test product and the reference product fall within the range 80-125%, even though the application of such criterion to drugs with high variability is controversial and regulatory agencies as strict as the FDA use different criteria. In Argentina, renowned specialists such as R. Bolaños, MD and S. Giarcovich, MD have analyzed the current status of the bioequivalence in the world proposing the most appropriate study designs.

Globally, drugs with high intra-individual variability are considered to be those with a coefficient of variation (CV) greater than 30% in pharmacokinetic parameters such as C_{max} and AUC. Different strategies have been tested given the high variability issue and in order to meet the conventional bioequivalence principles (90% CI 80-125). One has been to significantly increase the number of volunteers, sometimes to an unfeasible number, although this procedure does not guarantee that the results will fall within that equivalence interval. In this regard, there are reference products with high variability that are not capable of demonstrating bioequivalence with themselves. Additionally, the increase in volunteers to minimize variability poses an ethical problem, since we expose a greater number of healthy individuals to drugs that involve a risk in order to meet the bioequivalence criteria, which have been arbitrarily established. Other approaches have additional problems.

Given this difficulty, most regulatory agencies consider expanding the classical limits of bioequivalence (80-125%) in bioequivalence studies with drugs with high intra-individual variability. These considerations are made on the C_{max} and not on the AUC, where there is a consensus to keep the range 80 to 125% in all products. The reason for the greatest C_{max} variability compared to the AUC is the fact that this parameter arises from the measurement of an individual point, which makes it highly dependent on time, sampling frequency, and drug elimination rate.

Several proposals are available in the literature to modify the bioequivalence criteria for drugs with high variability. In general, the proposals are based on reducing the level of the confidence interval, on widening the equivalence limits, or on both.

A reduction in the level of the confidence interval, for example, from 90 to 85%, would imply a possible increase in the risk of patients, which is usually not acceptable. In contrast, the extension of the equivalence limits, which is the generally accepted criterion and the one used here for C_{max} , represents what limits are admissible and tolerable for the ratios (or differences) of the means between the compared products.

Any adjustment of these limits should be based on considerations of the statistical data properties, as well as the clinical characteristics of the individual drug. Statistically, the extension of the limits can be done by directly modifying the tolerated value of the bioequivalence limits, which is what some agencies such as the EMEA, Japan and South Africa have adopted. In countries like Canada, confidence limits for C_{max} are not required, but rather that the geometric mean ratios for T/R be within 80 -125%.

Using simulation techniques, Tothfalusi L et al.⁸ compared the gradual limit escalation for high variability drugs and the direct expansion of the limits around C_{max} . Escalation involves extending the limits of the confidence interval based on the variability of the reference product. Authors conclude that escalation would significantly reduce the sample size needed for bioequivalence studies of high variability drugs. They also conclude that the same results are obtained simply by extending the regulatory limits to 75-133% or even 70-143% for C_{max} .

To calculate the pharmacokinetic/pharmacodynamic parameters, specific pharmacokinetic software will be used (EquivTest version 2.0 (Equivalence Testing Software) from Statistical Solutions Ltd.)

Outliers: for measuring potential outliers, a selective statistical method will be applied. K&H Consulting S.A. will be responsible for statistical processing.

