PHARMACOKINETICS AND BIOLOGICAL ACTIVITY BETWEEN FORMULATIONS	
 - AUC_{0-12h}: area under the serum concentration curve between time 0 and 12 hours. - $AUC_{0-\infty}$: area under the serum concentration curve, as a result of the extrapolation between time 0 and infinite time. - C_{max}: maximum serum concentration of agalsidase beta. - T_{max}: time to maximum serum concentration for agalsidase beta. 
The difference between the T_{max} of the test formulation and that of the reference will be analyzed, and the drug elimination rate constant (Kel) and half-life ($t_{1/2}$) in the body will be calculated.
 
Summary measures (arithmetic and geometric means, standard deviation, CV% and range) for each formulation, as well as the individual results of each volunteer will be presented.

STATISTICAL ANALYSIS:	
SAMPLE SIZE CALCULATION:
 
The sample size ($n: 20$) was established based on data from the literature. As it is a sequential design, if the statistical analysis on the first 20 volunteers does not demonstrate bioequivalence, additional volunteers will be included for the eventual demonstration of bioequivalence with adequate power.

ANALYSIS PLAN	
COMPARATIVE PHARMACOKINETIC ANALYSIS BETWEEN FORMULATIONS
 
 - ABC_T / ABC_R: Ratio between the area under the curve for the Test formulation and the area under the curve for the Reference formulation. For log transformation, the 90% confidence interval of the AUC ratio (for AUC_{0-120h} and $AUC_{0-\infty}$) should be within the range of 0.80-1.25. - $C_{max\ T} / C_{max\ R}$: Ratio between the C_{max} of the Test formulation and C_{max} of the Reference formulation. For logarithmic transformation, the 90% confidence interval of the C_{max} ratio should initially be within the range of 0.80-1.25. 
COMPARATIVE ENZYME ACTIVITY ANALYSIS BETWEEN FORMULATIONS
 
 - Variation in the enzymatic activity for agalsidase beta in the sample at the end of infusion (5 h) compared to baseline (pre-infusion). For logarithmic transformation, the 90% confidence interval of the C_{max} ratio should initially be within the range of 0.80 -1.25. 
For an estimation of the pharmacokinetic parameters, specific pharmacokinetic computer softwares will be used (WinNonlin

Professional Edition, version 5.2.1 (2008).

Possible inter-subject and inter-treatment differences will be studied using ANOVA.

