4 STUDY DESIGN

Pharmacokinetics, biological activity and immunogenicity will be studied in 20 healthy volunteers starting with a single dose of 1 mg/kg/body weight after administration via intravenous infusion of one (1) dose of:

- Sanofi-Genzyme Fabrazyme®. (Reference Formulation, "R"), or
- Biosidus SA Agalsidase beta (Test Formulation, "T")

This study was conducted under an open, randomized, parallel-arm, balanced, and sequential design. As it is a sequential design, if the statistical analysis of the first 20 volunteers does not show bioequivalence, additional volunteers will be included until the similarity criterion is verified with adequate power.

For volunteers and clinical staff, the study is open. Laboratory determinations will be completed in a blinded fashion, with coded samples.

Below (Figure 1), a study visit scheme is presented:

[figure not shown]

Figure 1 Study Visit Scheme

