10 STATISTICAL CONSIDERATIONS AND ANALYTICAL PLAN. SAMPLE SIZE CALCULATION

A recent study with JR-051, the first agalsidase beta biosimilar to be approved in Japan, was conducted in 20 volunteers (10 per treatment group), based on the fact that previous studies with this molecule assumed the geometric mean of C_{max} and ABC_{0-24} with a value of 1.0 and a coefficient of variation of 0.15.

Therefore, with a power = 0.80, significance level $\alpha = 0.05$, and a limit for accepting bioequivalence where the 90% confidence interval of the AUC ratio (for AUC_{0-120h} and AUC_{0-24}) should be within the range of 0.80-1.25 9 volunteers per group are required for the study, estimating the possibility of 1 volunteer lost to follow-up per group, the sample size was calculated in 20 volunteers.

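### The Cmax limits may widen to 0.75-1.33 on a within-subject argument, but a parallel single-dose trial cannot estimate within-subject variability

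*Combined protocol and SAP*

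**What the plan says.** - **Acceptance rule (section 7.1.1).** The 90% CI of the Cmax ratio should first lie within 0.80-1.25. Then: "Considering the high intra-individual variability of this pharmacokinetic parameter, if a variability > 30% is confirmed, this interval" may be extended to 0.75-1.33. The same section defines highly variable drugs by an intra-individual CV above 30%.
- **Status of the rule (section 7.1.1).** It is operative, not background: "the extension of the equivalence limits, which is the generally accepted criterion and the one used here for" Cmax. AUC stays at 0.80-1.25.
- **Protocol Summary, Analysis Plan.** The Cmax interval "should initially be within the range of 0.80-1.25". The wider limits are not mentioned there.
- **Design (section 4).** The trial has an "open, randomized, parallel-arm, balanced, and sequential design". If the first 20 volunteers do not show bioequivalence, more are added, with no stated maximum.
- **Exposure (section 6.4).** "Each volunteer will receive only one study formulation (T or R) at visit II (Hospitalization").
- **Planning values (section 10).** Cmax and AUC geometric means are taken "with a value of 1.0 and a coefficient of variation of 0.15", giving 9 per group and 20 in total after one loss per group.

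**The concern.** The argument for wider limits in section 7.1.1 is about within-subject variability. Separating that from between-subject variability needs at least two administrations to the same person, and this trial gives one. Whatever CV is compared with 30% will be a total CV, which can be high because volunteers differ from one another.

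The trigger is also undefined. Section 7.1 reports a CV for each infusion, so a test, a reference and a pooled value will all be available, and the text does not say which counts, on what scale, or from what data. The extension is discretionary, and section 4.2 states that sponsor and investigator know each volunteer's treatment. Section 7.1.1 itself says any change of limits should reflect the clinical characteristics of the drug, yet gives no such argument for agalsidase beta. The claim of high variability also sits poorly with a planning CV of 0.15, half the trigger.

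At stake is whether a product at the edge of the standard Cmax margin can be declared similar more often than the 5% that margin allows.

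**Working it through.** **1. The plan's own figure.** Inputs from section 10: ratio 1.0, CV 0.15, α = 0.05 per side, power 0.80, limits 0.80-1.25. On the log scale σ = √ln(1 + CV²) = √ln 1.0225 = 0.149, with 2n − 2 degrees of freedom. Exact power of the two one-sided tests is 0.769 at n = 8 and 0.836 at n = 9 per group. The stated 9 per group is reproduced, at 0.80-1.25.

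**2. What the trial can estimate.** With one Cmax per volunteer, the residual variance is the between- plus the within-subject variance:

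total CV = √[(1 + CVw²)(1 + CVb²) − 1]

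Illustrative values (assumptions):
- CVw 10%, CVb 30%: √(1.01 × 1.09 − 1) = 31.8%
- CVw 15%, CVb 30%: √(1.0225 × 1.09 − 1) = 33.8%
- CVw 20%, CVb 25%: √(1.04 × 1.0625 − 1) = 32.4%

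Each exceeds 30% although within-subject variability is low by the plan's own definition.

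**3. How often the trigger fires at 10 per group.** Taking the pooled CV as trigger (an assumption), the probability is P[χ²(18) > 18 × ln 1.09 / ln(1 + CV²)].

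| True total CV | 0.15 | 0.20 | 0.25 | 0.30 | 0.35 |
|---|---|---|---|---|---|
| Trigger fires | 0.0% | 0.2% | 11% | 46% | 77% |

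The undefined estimator matters: with the CV of one arm alone, the rate is 17% at CV 0.25 and 67% at CV 0.35.

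**4. Cmax pass rate at a true ratio of 0.80.** Simulation of a log-normal parallel design with a 90% CI; limits 0.75-1.33 if the pooled CV exceeds 0.30, otherwise 0.80-1.25; one analysis only, with repeated looks not counted.

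| n per group | CV 0.30 | CV 0.35 | Fixed 0.80-1.25 |
|---|---|---|---|
| 10 | ≤5.0% | ≤5.0% | ≤5.0% |
| 20 | 9.4% | 12.6% | about 5% or less |
| 30 | 11.6% | 16.6% | about 5% or less |
| 40 | 13.6% | 20.2% | about 5% or less |
| 50 | 15.4% | 23.5% | about 5% or less |
| 100 | 24.1% | 37.9% | about 5% or less |

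At CV 0.25 the rates are 5.0-5.4% from 20 to 100 per group, and at CV 0.28 they are 7.3-8.5%. At a true ratio of 1.25 the pattern is the same: 9.1-22.9% at CV 0.30 and 12.2-35.8% at CV 0.35.

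There is no excess at 10 per group because the interval is too wide to fit. At CV 0.30, σ = 0.294 and the typical half-width is 1.734 × 0.294 × √(2/10) = 0.228, more than ln 1.25 = 0.223. At 20 per group it is 1.686 × 0.294 × √(2/20) = 0.157.

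**5. Overall claim, with AUC held to 0.80-1.25.** Assumptions: Cmax ratio 0.80, Cmax CV 0.35, AUC CV 0.25, log-correlation 0.8, one AUC standing for both.

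| n per group | 20 | 30 | 40 | 50 | 100 |
|---|---|---|---|---|---|
| AUC ratio 0.90, triggered rule | 11.6% | 16.1% | 19.9% | 23.3% | 37.8% |

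With fixed limits the AUC 0.90 case gives 4.0-5.0%. If the AUC ratio is also 0.80, the triggered rule gives 3.6-4.9%, so there is no excess over 5%. With correlation 0.5, the AUC 0.90 case gives 9.2-37.6%.

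**6. Which AUC case is likelier.** Section 1.1.3 gives a 300-minute infusion and a half-life of 80-120 minutes. Under a one-compartment assumption Cmax reaches 1 − 2^(−300/120) = 82% to 1 − 2^(−300/80) = 93% of plateau. Cmax and AUC therefore tend to move together, which favours the case without excess.

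**The case against.** The strongest reply is that harm needs three things the plan does not predict: a total CV near or above 0.30, twice the planning value; extension well beyond 10 per group; and a Cmax ratio further from 1 than the AUC ratio. The third is demanding. For Cmax 0.80 with AUC 0.90, the plateau fraction must fall by 0.80/0.90 = 0.889. Under the one-compartment model that moves a half-life of 80 minutes to about 120, or 120 to about 158, with a volume of distribution 46-67% larger. Extension to 100 per group is also hard to picture with two beds and a study of about six months.

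Secondly, under the written rule the limits above 30% are 0.75-1.33, so a ratio of 0.80 lies inside them. At the rule's own lower boundary of 0.75 the pass rate is 4.2-5.0% at CV 0.35 and 20-100 per group. The higher rates therefore mostly reflect the choice of a wider margin.

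Thirdly, section 7.2 sets an unwidened 0.8-1.25 criterion for end-of-infusion activity, which might catch such a product. The documents do not say whether it gates the overall conclusion.

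Finally, the required confirmation of variability could mean outside within-subject data, and the word 'initially' in the Summary proves little, since the enzyme-activity item uses it too.

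These points limit the size of the problem, and they stand for that purpose. They do not supply a trigger this design can evaluate. The wider margin is justified only by a quantity the trial cannot observe, and no outside estimate is cited.

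**Conclusion.** The concern holds and should be fixed. Section 7.1.1 makes the Cmax limits depend on a property that cannot be estimated with one infusion per volunteer, through an undefined trigger applied at discretion.

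The practical effect is conditional. It is nil at total CV 0.15, and does not exceed 5% at 10 per group for any CV tried (0.15-0.40). With total CV of 0.30-0.35 and an extended sample, the Cmax test at a true ratio of 0.80 passes at roughly two to four times the nominal rate for 20-40 per group (9.4-20.2%). Those Cmax-only rates are upper bounds on a false overall claim; the excess carries through only if AUC is nearer to 1 than Cmax, which may be the less likely case. The figures assume log-normal data, a pooled-CV trigger and a single analysis, and judge error against 0.80-1.25. Confidence is high on the mismatch between rationale and design, and lower on how often it would do harm.

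**What to change.** 1. In section 7.1.1, delete the sentence beginning "Considering the high intra-individual variability of this pharmacokinetic parameter, if a variability > 30% is confirmed, this interval" and the word 'first' in the sentence before it. Delete also the later clause naming extension as the criterion used in this trial for Cmax.
2. In the Protocol Summary, Analysis Plan, delete 'initially' from the Cmax item. The same word in the enzyme-activity item should go for consistency with section 7.2, which has no widening.
3. Insert in section 7.1.1: *The 90% confidence interval of the geometric mean Cmax ratio must lie within 0.80-1.25. These limits will not be widened, whatever variability is observed, and apply unchanged after any extension of the sample.* This fixes the limits only; the confidence level for repeated analyses needs its own rule.

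A single Cmax margin justified in advance and independent of the observed CV would also remove the defect, but the plan contains no such justification now.

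The cost is wording and the loss of a fallback. At total CV 0.30 and a true ratio of 1.0, the Cmax pass rate becomes about 8.5% instead of 17% at 10 per group, 52% instead of 69% at 20, and 79% instead of 89% at 30. At CV 0.15 nothing is lost: power at 10 per group is 88.4% either way.
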